2. The DSMB will perform several duties. First, they will review and approve research protocols and plans for data and safety monitoring prior to any study commencement. Second, they will evaluate the progress of any eligible trial. This will include assessment of data quality, participant recruitment, accrual and retention, participant risk versus benefit, and study outcomes. This assessment will be performed at meetings every six months during eligible trials and, more frequently, if decided by the DSMB. Third, they will make recommendations to ensure that all of the issues above are appropriately addressed. The corresponding project teams will be responsible for responding to all recommendations of the DSMB and submitting DSMB reports to the University of Pennsylvania IRB.

8. Data and Safety Monitoring Plan:

Oversight and evaluation will be accomplished using standard University procedures for safety monitoring. The specific elements of our oversight plan are as above: 1) all project staff will complete certification in the protection of research participants; 2) the principal investigator will supply the IRB with annual progress reports prepared for CURE as specified, or more frequently as determined by the IRB, which may in turn suspend, terminate or restrict the study as appropriate; 3) any serious adverse events will be reviewed in real time by the PI and reported to the IRB as required; and 4) the PI will inform CURE reviewers of any oversight actions taken by the IRB. The data and safety monitoring plan will have 3 parts. First, the study MPIs, biostatistician, and Director of the Data Management Unit will develop and implement methods of verifying entered data and of quality control. Second, the MPIs will be directly responsible for identifying and reporting all adverse events, protocol deviations/violations and unanticipated events to the IRB and funding agency promptly, as appropriate. The PIs will also report all adverse events, accrual rates, retention rates, and all other logistical issues to the DSMB (described above) at least biannually (and more frequently if there are serious adverse events). Third, there will be a DSMB responsible for monitoring the trial.

A written research protocol will undergo formal institutional scientific and institutional review board (IRB) review at the University of Pennsylvania (Penn) to ensure protection of the rights and welfare of human research subjects. Specifically, the MPIs and the IRB will be responsible for ensuring risks to human subjects are minimized, risks are reasonable, subject selection is equitable, the research team has access to adequate resources to conduct the study, the informed consent process (or waiver) meets regulatory and ethical requirements, adequate provision is made to protect human subjects by monitoring the data collected and there are adequate provisions to protect subject privacy per HIPAA regulations and confidentiality of data.

All senior/key personnel and research staff who will be involved in the design and conduct of the study must receive education in human research subject protection from a training program that is approved by a properly constituted independent Ethics Committee or Institutional Review Board. The MPIs will be responsible for ensuring project faculty and staff have the equipment and training required to protect privacy and confidentiality and will monitor and document that these individuals are properly certified. If new senior/key personnel and staff become involved in the research, documentation that they have received the required education will be included in the annual progress reports. The UPENN Office of Regulatory Affairs currently requires HIPAA

training upon designation as research investigator/staff and recertification in human research subjects protection every three years.

The Penn IRB will serve as the IRB of record for any external ethics review boards or IRBs applicable to researchers from other institutions who may have access to human research subjects identified data.

9. Investigator's Risk/Benefit Assessment:

This study presents minimal risk that is balanced by the potential benefits of the research to society.

INFORMED CONSENT:

1. Consent Process:

Aims 1 and 2. Since this is a pragmatic trial focused on improving implementation of higher-value evidence-based practices with minimal risk to patients, we are requesting a waiver of informed consent from clinicians and patients. We have received this in the past for these types of trials. We will identify clinicians at the practice sites and their patients using the EMR.

2. Waiver of Informed Consent:

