Penn ISC3 MPI [name] was integral to the efforts to formulate C3I, serving as a member of the NCI advisory board drafting and presenting the initiative to NCI leadership. ACC was in the first cohort of cancer centers selected for C3I. With this funding, the ACC's Tobacco Use Treatment Service (TUTS) was built by Penn ISC3 members Drs. [name], [name], [name], [name], and [name], and [name], based on the evidence-based *Ask-Advise-Connect* model.³⁰ This approach 1) systematically identifies smokers (Ask); 2) provides personal and persuasive advice to quit smoking (with attention to practical and emotional barriers; Advise); and 3) facilitates access to TUT, including counseling and FDA-approved medication through an EMR-based default (i.e., automatic referral; Connect). The approach involved standardizing a mandatory assessment of smoking status for all ACC patients, integrating cancer-relevant cessation advice in the written After Visit Summary, and building a fully automated electronic referral mechanism to Certified Tobacco Treatment Specialists that minimized disruption to workflow. Because the stressful dynamic of oncology practice may present additional barriers,³¹ we built in a process evaluating the suitability of TUT for integration into oncology workflow.

Evaluation shows the implementation strategy was promising, with room for improvement.

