Drs. [name] and [name] have evaluated Clinical Decision Support Tools for promoting the treatment of tobacco dependence in Penn primary care and CHOP practices, respectively. As noted in A.3., we will seek a waiver of informed consent. Aim 2 will not require additional participants; it will include data from all clinicians randomized to the RCT, as well as patient-level EMR data for all patients treated by the clinicians in the sample set during the study period. The trial is pragmatic in nature, assessing the impact of implementation strategies delivered to clinicians and patients through minor adjustments to existing workflow delivered through the electronic medical record (EMR). Changes to workflow are by necessity systematically applied to all clinicians within the practices, as well as their patients. We will obtain a waiver of informed consent for clinicians and patients for pragmatic trial activities accomplished for Aims 1 & 2.

We view this project as a quality improvement initiative (with data collection to allow for corresponding evaluations of the initiative). As a result, the changes introduced to the EHR (i.e., nudges to promote tobacco use treatment referral and engagement) will be considered standard of practice within the healthcare system, thereby allowing for a waiver of informed consent for both clinicians and patients. It is important to note that clinicians and patients involved in the project will not be assigned a change in treatment; clinicians are still free to refer or prescribe, or

not refer or not prescribe, as they see fit. Instead, they are being reminded of an evidence-based practice (EBP) guideline and offered an opportunity to review pertinent information and refer to and/or prescribe the EBP (or not) as clinically appropriate. Thus, the implementation strategies offer minimal risk to clinicians and patients. This approach to informed consent and data collection will also aid implementation integrity and generalizability by avoiding behavior changes related to being observed (i.e., the Hawthorne effect). In other words, this initiative could not practicably be carried out without the waiver as obtaining consent would introduce significant bias into the work, preventing the ability to achieve the aims and achieve the study goal: improving evidence-based tobacco use treatment within cancer care. We see this study as similar to those which have received waivers from our Institutional Review Board before.^{40,41}

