The Aim 1 primary measure of implementation is penetration (TUTS referral rate), defined as the number of TUTS orders signed, divided by the total number of pended orders (i.e., 1-cancellation rate). Our secondary measures of implementation include: prescription rate, defined as the number of pended orders accompanied by a signed prescription order for any of the seven FDA-approved medications for tobacco cessation, divided by the total number of pended orders; treatment engagement rates (medication), defined as the number of patients who make a pharmacologically-assisted quit attempt using any of the seven pharmacotherapies within 90 days of the initial oncology visit, divided by the total number of referred patients; treatment engagement rate (behavioral), defined as the number of patients who receive a quit-line referral or in-person or telephone cessation counseling, divided by the total number of TUTS-engaged patients; quit attempt rate, defined as the number of TUTS-referred patients who make any quit attempt, divided by the total number of TUTS-referred patients; and abstinence rate, defined as the total number of TUTS-referred patients self-reporting 7-day point prevalence abstinence at a 90-day follow-up assessment, divided by the total number of TUTS-referred patients. Established guidelines state that real-world pragmatic, population-based trials such as this do not require biochemical verification of abstinence and including it could introduce significant bias.⁴² Note, we will continue to monitor assessment rate (defined as the number of times the BPA is answered divided by the total number of times it fires) to ensure the intervention does not negatively impact assessment of tobacco use status by staff collecting vital signs or initially rooming the patients such as nurses, front desk staff, MAs, nursing assistants or technicians(baseline rate=90%).

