This is a pragmatic clinical trial focused on increasing use of TUTS. In all arms, clinicians can still choose what they like and patients can still decide to engage in TUTS or not. We will seek a waiver of informed consent for clinicians and patients. We will identify clinicians at the practice sites and their patients using the EMR. Patients will be required to meet the above outlined eligibility criteria. Clinicians (i.e., the unit of randomization) within each site will be randomized to four arms using variable permuted blocks. To control for confounding due to the fact that a small number of clinicians may potentially treat patients at multiple sites, clinicians will be randomized to arm irrespective of site.

We will use RCA to optimize implementation strategies to ensure face validity and maximum effect. We will focus on optimizing content, messaging, and design. RCA procedures involve design meetings with [name] and [name] and with discussions with administrators and clinicians who are members of our Implementation Lab. Clinicians and patients will be exposed to implementation strategies based on their assigned arm.

2. Study Intervention Phase:

Nudges to Clinicians. We will use the Best Practice Alert functionality within the EMR as our conduit to the point of decision-making. All sites use Epic (Epic Systems Corporation, Verona,

WI) to deliver care, or an interoperable system. Epic BPA deployment is modifiable, as we have done at the ACC (CA016520-41S4) and in primary care (DA045244). Epic currently “fires” a BPA for each new patient presenting to ACC within the check-in and vital sign workflow, requiring that staff collecting vital signs or initially rooming the patients such as nurses, front desk staff, Mas, nursing assistants or technicians assess tobacco use status within the past 30 days and satisfy the alert with one of three possible answers (CA016520-41S4). They then activate the “Order” tab for all patients identified as current smokers (i.e., within the past 30 days), resulting in placement of a pended order for consult to TUTS within the clinical workflow.

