We seek to improve TUTS referral and engagement by overlaying normative framed messages to address clinician and patient biases. Upon opening the Epic Order tab at a patient’s next visit after the screening encounter, clinicians will receive the implementation strategy, placed directly over the order interface. The clinician will be required to “acknowledge” or “opt-out” when presented with the order. Opting-out will require clinicians to acknowledge a reason for opt-out using a checklist or free text.

Nudges to Patients. Patients will receive a message sent through myPennMedicine following establishment of their smoking status (at the screening encounter). In all cases, the message will include information specific to the upcoming appointment with the oncology clinician.

Nudges to both clinicians and patients. Both strategies described above will be used.

Usual care. Clinicians and patients will receive no further interventions beyond usual practice. In early 2019, all Penn Medicine ACC clinicians receive the opportunity to refer to TUTS without nudges.

Message design and testing. Messages will be framed to undermine biases. We will optimize the framing of the messages using rapid-cycle approaches to ensure face validity and maximum effect

3. Data Collection:

The EMR and other Penn Medicine secondary databases (the TUTS program) will be used to collect information on practices, clinicians, and patients. These systems are used to routinely collect this information for patient care. We will also collect data from the census via publicly available datasets. Once collected, data are maintained on password-protected computers. [name], who directs the PENN DMS, will oversee the DMS for this study. ORACLE and MS ACCESS permit real-time data entry, storage, and QA by web-based remote access and scannable forms which increases standardization across personnel. We have >15 years of experience with this DMS for smoking cessation trials. The DMS generates database tables, constructs semantic constraints on fields, and is used for data entry, storage, retrieval, and security. The DMS uses visit dates to describe procedures and measures to be ascertained. The DMS mimics the appearance of CRFs which are completed at each visit. Each visit date is “milestoned” (e.g., completed, scheduled, missed). Clinician data will be ascertained by a survey conducted under a separate IRB protocol and funded by this grant.

4. Genetic Testing:

n/a

5. Use of Deception:

n/a

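### No Aim 1 outcome compares cessation medication by either route across all eligible patients: the prescription rate, as naturally read, leaves out medication reached through the referral

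*Combined protocol and SAP*

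**What the plan says.** METHODS, section 1 (Study Measures) lists the prescription rate among the secondary implementation measures. Its numerator is "the number of pended orders accompanied by a signed prescription order for any of the seven FDA-approved medications", and its denominator is all pended orders, signed or cancelled. No signer and no time window are given.

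Four other places bear on what this captures:

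- STUDY PROCEDURES, section 2 (Study Intervention Phase) shows that the pended order is a referral and not a drug order: identifying a smoker leads to activation of the order tab, "resulting in placement of a pended order for consult to TUTS within the clinical workflow".
- The Background account of the existing programme says that the approach "facilitates access to TUT, including counseling and FDA-approved medication through an EMR-based default".
- Under Subject Recruitment and Screening, referring and prescribing are separable acts. The clinician may "refer to and/or prescribe the EBP (or not) as clinically appropriate".
- The second medication outcome in Study Measures has this event and denominator: "pharmacologically-assisted quit attempt using any of the seven pharmacotherapies within 90 days of the initial oncology visit, divided by the total number of referred patients".

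The remaining treatment outcomes in Study Measures (behavioural engagement, quit attempts, abstinence) are divided by TUTS-engaged or TUTS-referred patients. METHODS, section 4 (Subject Follow-up) limits the 90-day telephone contact to referred patients.

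**The concern.** The clinician nudge sits on the TUTS order, and signing that order is the primary outcome. If it works, the expected path is a signed referral, then contact with TUTS, then possibly medication. Medication that starts after TUTS contact does not, on an ordinary reading, accompany the consult order. The prescription rate is the only treatment outcome not restricted to referred or engaged patients, yet on that reading it is blind to this path.

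The 90-day medication outcome does look at the path, but only within referred patients. Referral occurs after randomisation and is what the nudges are designed to increase, so its denominator can differ in composition between arms. It also says nothing about patients who were not referred.

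H1a under OBJECTIVES concerns engagement as well as referral. At stake is whether the trial can say if more of its eligible patients were treated with medication. As written, it could report flat prescribing when medication treatment had risen.

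**Working it through.** The documents give no prescribing rate, expected effect or power for this outcome, so there is no stated figure to reproduce. The check is an accounting identity, taking one pended order per patient.

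**Inputs**

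- R, the referral rate: 34% under usual care and 45% as the target (section 6, Statistical Analysis).
- a, the probability of a prescription signed with the order, given referral: assumed.
- b, the probability of a prescription, given no referral: assumed.
- m, the probability of medication later through TUTS, given referral and none signed with the order: assumed.

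**Formulas**

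- Rate as defined = R·a + (1 − R)·b
- Any medication = R·[a + (1 − a)·m] + (1 − R)·b

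When R rises by 11 points, the rate as defined changes by 0.11·(a − b), whatever m is. Any medication changes by 0.11·[a + (1 − a)·m − b].

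**Results, usual care → nudge arm**

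| a | b | m | Rate as defined | Any medication |
|---|---|---|---|---|
| 10% | 10% | 20% | 10.0% → 10.0% (0) | 16.1% → 18.1% (+2.0) |
| 10% | 10% | 40% | 10.0% → 10.0% (0) | 22.2% → 26.2% (+4.0) |
| 10% | 10% | 60% | 10.0% → 10.0% (0) | 28.4% → 34.3% (+5.9) |
| 20% | 10% | 30% | 13.4% → 14.5% (+1.1) | 21.6% → 25.3% (+3.7) |
| 5% | 10% | 30% | 8.3% → 7.75% (−0.55) | 18.0% → 20.6% (+2.6) |
| 10% | 20% | 10% | 16.6% → 15.5% (−1.1) | 19.66% → 19.55% (−0.11) |

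For example, row 2 under usual care is 0.10 + 0.90 × 0.34 × 0.40 = 22.2%, and in the nudge arm 0.10 + 0.90 × 0.45 × 0.40 = 26.2%.

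The rows show three patterns:

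- With equal prescribing in referred and non-referred patients (a = b), the gain is missed.
- With more prescribing in referred patients (a > b), the direction is right but the gain is understated.
- With less (a < b), the rate falls. Any medication still rises if a + (1 − a)·m exceeds b, as in row 5, and otherwise does not, as in row 6.

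**Substitution.** Suppose nudged clinicians hand one in five of their own prescriptions to TUTS, with the row 2 inputs. The rate as defined goes from 10% to 8%. Any medication in the nudge arm is 0.08 + 0.02 × 0.40 + 0.90 × 0.45 × 0.40 = 25.0%, against 22.2% under usual care (+2.8 points).

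**The companion outcome.** Suppose 40% of usual-care referred patients make a drug-assisted quit attempt, and 20% of the extra 11 points of referrals do. Per referred patient, the result goes from 40.0% to (0.34 × 0.40 + 0.11 × 0.20)/0.45 = 35.1%. Per pended order, it goes from 0.34 × 0.40 = 13.6% to 15.8%. The reported outcome falls while use among all patients with an order rises.

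**The case against.** Four arguments count against the point.

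- **The wording is open.** The definition names no signer, visit or window, so a restriction to prescriptions the oncology clinician signs at the visit is a reading, not text. The documents also do not say who signs prescriptions after referral. This stands. The natural reading excludes later medication, but what is certain is that the link between prescription and order is undefined.

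- **The plan divides the work.** The prescription rate can be taken as a measure of what clinicians do with the order, and the 90-day outcome covers what follows referral. The first half stands: it is a legitimate secondary process measure. The second stands in part. Multiplying the companion outcome by the referral rate gives referral-linked use per pended order. With the row 2 inputs, and if every medicated patient makes an assisted attempt, P(medication given referral) = 0.10 + 0.90 × 0.40 = 0.46, so 0.46 × 34% = 15.6% against 0.46 × 45% = 20.7%. A reader might infer that the whole outcome set would show nothing, and that would be wrong. But the product is not a planned analysis, needs both outcomes on the same unit, and omits prescriptions to non-referred patients (0.10 × 66% = 6.6% against 0.10 × 55% = 5.5%). Its 5.1-point difference is therefore not the 4.0-point difference in all patients.

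- **The sizes are assumed.** Setting a = b fixes the zero in advance. True, and if m is 0 there is no gap at all.

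- **A recorded loss is speculative.** A reader might infer that the prescription rate is likely to fall when treatment rises. The documents do not support this. It needs clinicians to replace prescribing with referral, or to prescribe less often to referred patients, with enough later TUTS medication to outweigh it. Nothing in the description of the nudge discourages prescribing, and no rates are given.

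**Conclusion.** The concern holds in a limited form. On its natural reading, the prescription rate does not credit medication reached later through the referral, and the companion outcome is conditioned on referral. No Aim 1 outcome therefore compares medication by either route across arms in all eligible patients.

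The prescription rate can miss or understate a gain. Under the assumed 10% same-order prescribing in both arms and 20% to 60% later uptake, a gain of 2 to 6 points appears as zero. These figures illustrate the mechanism and do not forecast the result; only the 34% and 45% come from the plan. A recorded loss is arithmetically possible under the extra conditions above, which the documents do not quantify.

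The measure is secondary and the primary outcome is unaffected. The change is worth making because it is cheap and gives the trial a medication outcome that does not depend on referral.

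**What to change.** Keep the prescription rate as a process measure of clinician prescribing, and state who must sign and within what window for a prescription to count as accompanying the order.

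Add one secondary outcome: the proportion of all patients in the intention-to-treat cohort of section 6 (Statistical Analysis) with a signed order for, or TUTS-recorded supply of, any of the seven medications, from the Step 3 visit to 90 days after it. Analyse it with the same GEE logistic model.

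The sources are already in the plan. STUDY PROCEDURES, section 3 (Data Collection) says: "The EMR and other Penn Medicine secondary databases (the TUTS program) will be used to collect information on practices, clinicians, and patients". The cost is one outcome definition and one data query, with no added patient contact.

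The new outcome will count some prescriptions unrelated to the oncology visit, which is a reason to keep the same-order rate beside it. It will also miss medication obtained outside Penn, and it records orders and supply, not use.
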